14.3 Statistical Analysis Endpoints

14.3.1 Primary Endpoint

Incidence of hernia recurrence within 12 months will be calculated on the FAS subjects who reach the 12-month follow-up including any subject with hernia recurrence diagnosed within the 12-month period following surgery (even if the subject has withdrawn from the study before the 12-month assessment).

The primary endpoint will be summarized using count, percentage, and the corresponding 95% confidence interval. Sub-group analyses on primary endpoints will be performed according to study needs and will be described in the Statistical Analysis Plan and the Clinical Study Report.

14.3.2 Secondary Endpoints

- Incidence of ADEs intra-operatively will be calculated on the FAS subjects who reach the corresponding time point, including any subject experiencing hernia recurrence, AEs or ADE within the corresponding follow-upperiod.
- Incidence of hernia recurrences will be calculated on the FAS subjects who reach the corresponding time point.
- Time to hernia recurrence, as well as time to AE occurrence analyses will be run using Kaplan Meier estimate and curve.
- Subject quality of life (QoL) questionnaires will be evaluated using the Carolinas Comfort
 Scale™ (Appendix B), and statistical analysis will follow the corresponding analysis guideline.
- Length of hospital stay will be summarized using count, mean, standard deviation, median, minimum, and maximum.

Subgroup analyses on secondary endpoints will be performed according to study needs and will be described in the statistical analysis plan and the clinical study report.

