5.2.2 Secondary Endpoint

The secondary endpoints will include:

- Incidence of adverse device effects (ADEs) intra- operatively, at discharge, within 1-month, 3-months, 12-months, and 24-months following Parietene™ DS Composite Mesh use in ventral hernia repair
- Incidence of hernia recurrence at 1, 3 and 24 months. The evaluation of hernia recurrence will be performed during a physical examination

MDT17051PDS Version 4.0 Page 16 of 56

- Time to hernia recurrence and time to adverse device effect occurrence (from surgery time- point)
- Carolinas Comfort Scale™ QOL questionnaire completed pre-operatively and at 1, 12 and 24 months post-operatively (Section 17.2)

6. Study Design

This study is a USA based, single arm, prospective, multi-center, observational investigation to confirm the clinical safety and performance of Parietene™ DS Composite Mesh in ventral hernia repair.

After IRB approvals, subjects who have signed an informed consent form (who meet the eligibility criteria) and have received Parietene™ DS Composite Mesh will be enrolled in the study. Subjects will undergo elective ventral hernia repair using Parietene™ DS Composite Mesh and be evaluated preoperatively, at the procedure, at discharge, within 1-month, 3-months, 12-months, and 24-months post-surgery.

An interim analysis based on 30 subjects with completed 3-month visits will assess the short-term safety of the device and will be used to support regulatory submission. Study enrollment will continue during interim analysis. The study will continue as a post market clinical follow-up (PMCF) with extended follow-up of subjects to assess the mid (12-months) and long (24-months) term safety and performance of the device. The study will include a minimum of 125 subjects in a minimum of 4 sites who will be followed 24 months post-surgery.

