10.12.3 Study Exit

A study exit eCRF is required for all subjects. Prior to exiting a subject from the study, it is recommended to follow the subject until all ongoing system and/or procedure related AEs are resolved or unresolved with no further actions planned. All data available through the time of the subject's exit will be used for analysis.

MDT17051PDS Version 4.0 Page 31 of 56

Subjects are urged to remain in the study as long as possible but may be exited from the study for any of the following situations:

- Study completed
- Subject lost to follow-up
- Subject death
- Subject did not meet inclusion/exclusion criteria
- Subject was not implanted with a (investigational) device
- Subject did not provide consent <or data use protection authorization>
- Subject chooses to withdraw (e.g., consent withdrawal, relocation to another geographic location)
- Investigator deems withdrawal necessary (e.g., medically justified, inclusion/exclusion criteria not met, failure of subject to maintain adequate study compliance)

If discontinuation is because of safety or lack of effectiveness, the subject may be asked to be followed for collecting safety data outside the clinical investigation.

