10.12.4 Withdrawal

The reason for study exit will be documented on the applicable eCRFs. In the event the subject withdraws consent during the study, the date of withdrawal will be documented. If the study Investigator(s) voluntarily removes a subject from further study participation, supporting documentation must be in place for the rationale and date of removal. Follow-up of subjects withdrawn will be determined by investigator(s). Withdrawn subjects will be not replaced.

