14.2 Interim Analysis

Preliminary analysis will be conducted in the study when 30 enrolled subjects complete the 3-month follow-up time-point. The objective is to confirm safety of the product at 3 months. This 3-month time-point is consistent with the wound healing period and the Parietene™ DS Composite Mesh film degradation profile (completely degraded by bulk hydrolysis in less than 15 weeks). This interim analysis is driven by regulatory needs, to support CE marking submission.

Through analysis of clinical data available on a predicate device (Proceed™ surgical mesh) and similar Medtronic composite meshes (Parietene™ Composite Mesh, Parietex™ Composite Mesh) used in ventral hernia repair (primary and incisional) by open or laparoscopic approach assessed during short-term post-surgery report the following adverse event rates:

- 10.6% on the equivalent, Proceed™ surgical mesh used in laparoscopic ventral hernia repair at 3-6 weeks follow-up (9),
- 14.3% on Parietene™ Composite mesh used in laparoscopic ventral hernia repair at 10 weeks follow-up (range 6-25 weeks) (10),
- To 25%, on Parietex™ Composite mesh used in laparoscopic and open ventral hernia repair after
 2 months follow-up with a population of 30 subjects (11), we obtain the following binomial probabilities to observe one or more event(s):

[figure not shown]
Based on these studies, adverse event rates were estimated to range between 11% and 25% and used to generate binomial probabilities to observe at least 1 or 2 AEs with a sample size of 30 subjects as shown in the table below.

N=30 subjects	Hypothetic procedure related adverse event rate						
prob. to observe:	11%	12%	14%	17%	20%	25%	
≥ 1 AE	97.0%	97.8%	98.9%	99.6%	99.9%	100.0%	
≥ 2 AEs	85.7%	89.0%	93.6%	97.3%	98.9%	99.8%	

With an N=30 of enrolled and evaluable subjects at the time of interim analysis, and assuming an 11% adverse event rate, there is a 97% probability to observe at least 1 adverse event and an 85.7% probability to observe at least 2 adverse events. In addition, the probability to observe adverse events increases as the adverse event rate increases to a maximum of 100% and 99.8% for observation 1 and 2 adverse events respectively at an adverse event rate of 25%.

An additional interim analysis is planned to occur for completed 12-month follow-up visit data.

MDT17051PDS Version 4.0 Page 42 of 56

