14.5 Sample Size Determination

Sample size has been determined based on an acceptable level of accuracy for the estimated rate of hernia recurrence at 12 months (primary endpoint).

Previous studies of the predicate device (Proceed™ Surgical mesh) with similar study indications, population, and design (prospective study with a long-term follow-up with more than 100 subjects), have reported the incidence of recurrence at 12 months to range from 3.5% to 5.2%. (8, 9).

95% confidence intervals obtained from incidence rates between 3.5% and 5.2% with N=100 subjects are shown below. Precision of the recurrence rates range from \pm 3.6% to \pm 4.4% as the recurrence rate increases.

	Recurrence rate at 12-month (1 year)						
	3.5%	4.0%	4.5%	5.2%			
N	100	100	100	100			
95% CI	[0.0 % - 7.1 %]	[0.2% - 6.7%]	[0.4% - 8.6%]	[0.8% - 9.6%]			
accuracy (+/-)	3.6%	3.8%	4.1%	4.4%			

Anticipating an attrition rate of 20% at 12 months, 125 subjects will be enrolled for this study.

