7.9. Evaluation of Objectives

Study objectives will be assessed through study endpoints measurement.

The primary endpoint is incidence of hernia recurrence within 12 months following Parietene[™] DS Composite Mesh use in ventral hernia repair.

Incidence of hernia recurrence within 12 months will be measured on the FAS subjects and using the following calculation formula:

[Subjects with Recurrence diagnosed within the first 12month following surgery]

[Subjects with Recurrence diagnosed within the first 12month following surgery + Subjects free of recurrence with a follow-up ≥12months]

A confirmatory analysis of primary endpoint will be run using Per Protocol Analysis Set.

Secondary endpoints

- Incidence of adverse device effects (ADEs) intra-operatively, at discharge, within 1 month, 3 months, 12 months, and 24 months following Parietene[™] DS Composite mesh use in ventral hernia repair will be primarily assessed based on FAS, and secondarily using PPAS and SAS.
- Incidence of hernia recurrence at 1, 3 and 24 months. The evaluation of hernia recurrence will be performed during a physical examination, using the formula described previously, according to the different time-points, and based on FAS and PPAS.
- Time to hernia recurrence and time to adverse device effect occurrence (from surgery time-point), will be assessed using Kaplan Meyer estimates. FAS and PPAS will be used for time to hernia recurrence, while FAS, PPAS and SAS will be used for time to ADE occurrence analysis. Time to Device-related AEs occurrence may also be assessed using Kaplan Meyer estimates.
- Carolinas Comfort Scale[™] QOL questionnaires completed pre-operatively and at 1, 12 and 24 months postoperatively will be analyzed using the Carolina Comfort Scale User Guide recommendations and programming code (see Appendix B), and based on FAS and on PPAS.

Several Subgroup analyses will be performed. Comparative analyses will be performed by hernia type (primary hernia versus incisional hernia) on overall subjects and on a subgroup of subjects with robotically assisted laparoscopic repair. Results of subjects operated with robotically assisted laparoscopic repair will also be compared with subjects operated with a traditional Laparoscopic procedure.

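### The ADE incidence denominator depends on outcome in protocol 14.3.2 and has no formula in the SAP; each available reading can bias the 12- and 24-month rates, in opposite directions.

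*Protocol*

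**What the plan says.** Protocol 5.2.2 lists ADE incidence first among the secondary endpoints, intra-operatively and then "at discharge, within 1-month, 3-months, 12-months, and 24-months following" mesh use. Protocol 14.3.2 gives the calculation: ADE incidence "will be calculated on the FAS subjects who reach the corresponding time point, including any subject experiencing hernia recurrence, AEs or ADE" within the matching period. That bullet mentions only the intra-operative time.

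Protocol 14.1 limits the term adverse event, for analysis, to procedure-related events and ADEs. Protocol 14.4 says that the methods for most safety endpoints have already been described. It then names the FAS, SAS and PPAS for ADE incidence, with counts and percentages.

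SAP 7.9 says that ADE incidence "will be primarily assessed based on FAS, and secondarily using PPAS and SAS". It gives an explicit formula for recurrence within 12 months and reuses it for recurrence at the other visits, but gives none for ADEs. SAP 7.10 reports the proportion of subjects with an AE on the same three sets. SAP 7.12 lists changes to the analysis sets and their use, and none to this denominator.

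Time to ADE is a separate secondary endpoint, which "will be assessed using Kaplan Meyer estimates". Protocol 10.12.3 adds: "All data available through the time of the subject's exit will be used for analysis".

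**The concern.** Under 14.3.2, a subject who leaves early after a qualifying event stays in the fraction, while one who leaves early without an event is removed. Membership of the denominator therefore depends on outcome, and early ADEs are divided by a shrinking number as event-free subjects leave. The rule also keeps early leavers whose only event was a recurrence or a procedure-related AE that is not an ADE. They enlarge the denominator and partly offset the inflation.

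If the SAP is read instead as meaning the whole FAS, every leaver is counted as ADE-free for the rest of follow-up. That does little harm if ADEs come early but understates the rate if they come late. On the SAS there is a further difficulty: subjects who fail screening during surgery are followed only to discharge (protocol 10.12.2.2).

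Two statisticians could thus report different 12- and 24-month ADE rates from the same data, each following the plan, in a study meant to confirm mid- and long-term safety.

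**Working it through.** **Inputs**

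- Attrition at 12 months: "Anticipating an attrition rate of 20% at 12 months, 125 subjects will be enrolled for this study" (protocol 14.5). The plan's figure reproduces: 100/(1 − 0.20) = 125.
- Attrition at 24 months: not stated. I assume the same yearly rate: 1 − 0.80 × 0.80 = 36%. Leavers are not made up: "Withdrawn subjects will be not replaced" (protocol 10.12.4).
- ADE rate: not stated. In protocol 14.2, "adverse event rates were estimated to range between 11% and 25" percent, but the table there labels this a procedure-related AE rate. I use 5% and 11% as illustrations.
- Other early procedure-related AE: 25% of subjects, independent of ADEs (assumed).
- Drop-out: constant rate, unrelated to ADEs (assumed).

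**Which times the rule covers.** Every FAS subject reaches the intra-operative time, so a condition about reaching a corresponding time point would be empty if it applied only there. It makes sense for the list in 5.2.2. Protocol 14.3.1 uses the same construction for recurrence at 12 months.

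**A count example.** Let 10 of 125 subjects have an ADE before 3 months and none later, with all drop-out after that. The true rate is 10/125 = 8.0%. At 12 months, 25 subjects have left.

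- Only ADE subjects retained: 25 × 115/125 = 23 event-free leavers are removed; 10/102 = 9.8%.
- 31 subjects with any qualifying event: 25 × 94/125 = 18.8 removed; 10/106.2 = 9.4%.
- 50 such subjects: 25 × 75/125 = 15 removed; 10/110 = 9.1%.
- All 25 leavers event-free: 10/100 = 10.0%.

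Whole FAS and Kaplan-Meier both give 8.0%.

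**All ADEs in month 1.** With true rate p, attrition a and a fraction q with another retained event, the protocol rule gives about p / [p + (1 − p)(1 − a(1 − q))].

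- p = 5%, q = 25%: 0.05/0.8575 = 5.8% at 12 months; 0.05/0.7435 = 6.7% at 24.
- p = 11%, q = 25%: 0.11/0.8665 = 12.7%; 0.11/0.7597 = 14.5%.
- p = 11%, q = 0: 0.11/0.822 = 13.4%; 0.11/0.6796 = 16.2%.

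The formula puts every event before any drop-out. Integrating numerically, with events spread over days 0 to 30 and drop-out from day 0, lowers each 11% figure by about 0.1 point; the table shows those values.

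**Half of ADEs late.** Half fall in days 0 to 30 and half are spread evenly from surgery to day 730. The mean fraction still in the study is 0.991 over the first 30 days and 0.36/(−ln 0.64) = 0.807 over 730 days. Observed ADE subjects as a share of the FAS:

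- p = 11%: 5.5 × 0.991 + 5.5 × 0.807 = 9.9%.
- p = 5%: 2.5 × 0.991 + 2.5 × 0.807 = 4.5%.

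These are the whole-FAS results. The protocol rule divides the same counts by those who reach 24 months or have a qualifying event, about 74.9 and 73.8 per 100 enrolled. That gives 13.2% and 6.1%.

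| ADE timing | True | Protocol rule, 12 m | Protocol rule, 24 m | Whole FAS, 24 m |
|---|---|---|---|---|
| Month 1 | 5% | 5.8% | 6.7% | 5.0% |
| Month 1 | 11% | 12.6% | 14.4% | 10.9% |
| Month 1, q = 0 | 11% | 13.3% | 16.1% | 10.9% |
| Half late | 5% | – | 6.1% | 4.5% |
| Half late | 11% | – | 13.2% | 9.9% |

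Kaplan-Meier estimates the true value in each row because drop-out was assumed unrelated to ADEs.

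**The case against.** The strongest reply is that the plan may never apply the 14.3.2 rule beyond surgery. The bullet names only the intra-operative time, protocol 14.4 and SAP 7.9 and 7.10 name whole analysis sets, and the SAP attaches its reach-the-time-point formula to recurrence alone. On a whole-FAS reading the rate cannot rise without new ADEs. A reader might infer from 14.3.2 that the reported rate is bound to climb with drop-out; the documents do not settle that. What stands is that 14.4 also refers back to the earlier method, no ADE formula replaces it, and the alternative reading has its own bias.

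Second, the unbiased analysis is already planned. That is true, and early leavers' data do enter it, so it would be too strong to say that their data are discarded contrary to 10.12.3. But time to ADE is a separate endpoint, and nothing makes it the reported incidence at each visit.

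Third, the effect is modest. At a true 5% with 125 subjects the 95% half-width is 1.96 × √(0.05 × 0.95/125) = 3.8 points, more than any shift shown for 5%. Remote and record-based follow-up (protocol 10.6) may also keep attrition below 36%. Both are fair, but the shift is systematic and avoidable.

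Finally, one might think that any AE keeps a leaver in the denominator. Protocol 14.1 excludes wholly unrelated events.

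**Conclusion.** The concern holds as an inconsistent and incompletely specified ADE denominator. The rule written in 14.3.2 inflates the 12- and 24-month rates when event-free subjects leave; the whole-FAS reading understates them when ADEs occur after some subjects have left. The documents do not establish which would be used, so neither direction should be presented as certain.

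For a true 11%, the 24-month figure lies between 9.9% and 14.4% depending on reading and ADE timing, or up to 16.1% if no subjects with other events are retained. For a true 5%, the range is 4.5% to 6.7%. Only the 20% attrition is the plan's; the 24-month attrition, ADE rates, timing, share with other events and uninformative drop-out are assumptions. It would be wrong to read the 11% to 25% range in protocol 14.2 as an expected ADE rate. This affects a secondary safety estimate and should be corrected; it does not touch the primary endpoint or the sample size.

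**What to change.** In protocol 14.3.2, replace the whole denominator phrase, from "will be calculated on the FAS subjects who reach the corresponding time point, including any subject experiencing hernia recurrence, AEs or ADE" to the end of that sentence. Removing only the clause about subjects with events would leave a completers-only denominator. Restore the time points from 5.2.2 and put the same definition in SAP 7.9. Suggested content:

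- ADE incidence within 1, 3, 12 and 24 months is the Kaplan-Meier estimate 1 − S(t) with its 95% CI, using ADE onset date and censoring at last contact, shown beside the number of subjects with an ADE.
- Intra-operative and discharge incidence is the simple proportion of all FAS subjects, and of all SAS subjects.

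Record the change in SAP 7.12. Kaplan-Meier assumes that censoring is unrelated to ADE risk, so list exits by death or for device-related reasons alongside.

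The cost is wording in two documents. The Kaplan-Meier ADE analysis is already planned on FAS, PPAS and SAS, so the change only designates which figure is the incidence estimate and tabulates it at the visit times.

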14.4 Safety Assessment

Most of the safety endpoints are part of secondary endpoints and method of evaluation are described above.

Incidence of Adverse device effect, as well as SAEs, and SADEs will be calculated on the Full Analysis Set, Safety Analysis Set and Per protocol Analysis Set and summarized by counts and percentages.

MDT17051PDS Version 4.0 Page 43 of 56

Listings of AEs will be generated including event description, severity and seriousness, relation to procedure, relation to the device and outcome.

In the case that a subject becomes pregnant postoperatively, a deviation will be submitted, and they will be followed for safety assessment. They will not be included in the primary or secondary endpoint analyses.

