14.1 Statistical Test Methods & Analysis Populations

Statistical analysis consists mainly of a descriptive analysis, and will be performed on:

- the Full Analysis Set (FAS, including any subject enrolled and receiving study device) representing the primary analysis population,
- the Per Protocol Analysis Set [PPAS, a subset of the FAS of subjects who meet the primary endpoint (12-month assessment) and who did not deviate (major) from the protocol], as confirmatory analysis and,
- the Safety Analysis Set (any subject with skin incision including those who are 'screen failure during surgery') for safety and efficacy analysis

Continuous variables will be summarized using counts, means, standard deviations, medians, minimum and maximum. Categorical variables will be summarized using frequencies and percentages.

Time to events analyses using Kaplan Meier estimates and curve will be performed for time to recurrence or to adverse event occurrence

Changes to the planned statistical analysis as defined in the protocol will be documented in the statistical analysis plan and clinical study report.

Statistical analysis will be performed using SAS version 9.4 and Minitab® Version 15.0.

MDT17051PDS Version 4.0 Page 41 of 56

For the purposes of study analysis and statistics adverse event will be defined as procedure related adverse events and adverse device effects.

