7.1.3. Analysis Sets

Statistical analysis will be performed on:

- Full Analysis Set (FAS): including any subject enrolled and receiving study device, representing the primary analysis population, for Efficacy and Safety analyses
- Per Protocol Analysis Set (PPAS): a subset of the FAS of subjects who meet the primary endpoint (12month assessment) and who did not deviate (major) from the protocol, as confirmatory analysis for Efficacy and Safety analyses,
- Safety Analysis Set (SAS): any subject pre-operatively eligible with skin incision including those who are 'screen failure during surgery', used for Safety analysis.

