7.8.2. Second Interim Analysis

A second interim analysis is planned to occur when all enrolled subjects complete the 12-month visit, to assess both primary and secondary endpoints, when possible.

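### Protocol 14.4 excludes subjects who become pregnant after surgery from the primary and secondary endpoints with no time limit, which conflicts with Protocol 14.3.1 and the SAP

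*Protocol*

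**What the plan says.** Protocol 14.4 (Safety Assessment) sets the trigger: "In the case that a subject becomes pregnant postoperatively, a deviation will be submitted, and they will be followed for safety assessment". The next sentence sets the consequence: "They will not be included in the primary or secondary endpoint analyses". No window, censoring date or exception for earlier visits or events is given.

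The rest of the plan points the other way:

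- Protocol 14.3.1 builds the primary endpoint on full analysis set (FAS) subjects who reach 12 months, "including any subject with hernia recurrence diagnosed within the 12-month period following surgery", and adds that this holds even for subjects who withdrew before the 12-month assessment.
- SAP 7.1.3 defines the FAS as "including any subject enrolled and receiving study device, representing the primary analysis population, for Efficacy and Safety analyses". Pregnancy is not mentioned.
- SAP 7.9: "Incidence of hernia recurrence within 12 months will be measured on the FAS subjects and using the following calculation formula". The formula divides recurrences within 12 months by those recurrences plus recurrence-free subjects followed for at least 12 months. It has no pregnancy term.
- SAP 7.12, which lists changes from the protocol, does not mention the pregnancy rule.

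On timing, SAP 7.8.2 states: "A second interim analysis is planned to occur when all enrolled subjects complete the 12-month visit, to assess both primary and secondary endpoints, when possible". Follow-up then runs on to 24 months.

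**The concern.** The exclusion depends on something that happens after surgery, and it applies to the subject rather than to the data collected after the pregnancy. Three things follow if it is applied as written.

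- An observed failure can leave the primary endpoint. A woman with a recurrence at month 3 who becomes pregnant at month 20 is no longer counted, whereas one who recurs at month 3 and then withdraws is.
- The 12-month rate is not fixed once month 12 is complete. A pregnancy between months 12 and 24 removes someone who was counted at the second interim analysis, so the same quantity can differ at the final analysis for a reason outside its own window.
- ADE incidence from the operation to 24 months is a secondary endpoint (Protocol 5.2.2), so even an intra-operative ADE drops out of that endpoint.

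Because the SAP does not carry the rule, an analyst following the protocol and one following the SAP could report different primary results if such a subject exists.

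**Working it through.** **1. The plan's own figures.** Protocol 14.5 and SAP 6 assume 100 evaluable subjects, a 12-month recurrence rate of 3.5% to 5.2%, and 20% attrition. The half-width 1.96 × √(p(1−p)/100) gives 3.60, 3.84, 4.06 and 4.35 points at 3.5%, 4.0%, 4.5% and 5.2%, matching the printed 3.6, 3.8, 4.1 and 4.4. Enrolment is 100/(1 − 0.20) = 125, as stated. About 4 to 5 recurrences are therefore expected in 100 evaluable subjects.

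**2. One hypothetical subject under each text.** She recurs at month 3, becomes pregnant at month 20 and completes follow-up.

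| Text | In the 12-month numerator? | In the denominator? |
|---|---|---|
| Protocol 14.3.1 | Yes | Yes |
| SAP 7.9 formula on the SAP 7.1.3 FAS | Yes | Yes |
| Protocol 14.4, as written | No | No |

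At the second interim analysis she is counted under all three, provided her pregnancy comes after that analysis. At the final analysis she is counted under only two.

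**3. Size of the shift.** Take x recurrences in n evaluable subjects. Removing k pregnant subjects, r of whom had recurred, changes the rate from x/n to (x − r)/(n − k). The documents do not give k or r; the values below are assumptions.

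| Before removal | One subject who recurred removed (k=1, r=1) | One recurrence-free subject removed (k=1, r=0) |
|---|---|---|
| 4/100 = 4.00% | 3/99 = 3.03% (−0.97) | 4/99 = 4.04% (+0.04) |
| 5/100 = 5.00% | 4/99 = 4.04% (−0.96) | 5/99 = 5.05% (+0.05) |
| 5/125 = 4.00% | 4/124 = 3.23% (−0.77) | 5/124 = 4.03% (+0.03) |

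Over a wider range, starting from 4/100, two subjects who both recurred give 2/98 = 2.04%, and five recurrence-free subjects give 4/95 = 4.21%.

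**4. Precision.** At 5.2%, the half-width goes from 4.35 points at N=100 to 4.46 at N=95. What matters is losing an event; the smaller N hardly counts.

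**5. How often an event would be lost.** If recurrence is independent of pregnancy (an assumption), one pregnant subject has a 3.5% to 5.2% chance of having recurred within 12 months. For at least one of two, the chance is 1 − 0.965² = 6.9% to 1 − 0.948² = 10.1%.

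**The case against.** The strongest reply is that this is a narrow drafting conflict with little numerical effect. Much of that stands.

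- A reader might infer that the plan expressly deletes recurrences seen before the pregnancy. It does not: 14.4 never mentions earlier events. Their loss follows from a whole-subject exclusion with no time limit, and the SAP read literally would keep them. What the documents establish is an unresolved conflict.
- A reader might infer that a published 12-month rate would be revised. SAP 7.8.2 plans an analysis at that point but does not say that its result is released.
- A reader might infer that device safety data are lost. Protocol 14.4 keeps these subjects under safety follow-up. SAP 7.10 reports adverse event incidence by relation to device and by seriousness on the full, per-protocol and safety sets, with listings, and has no pregnancy exclusion. The loss is confined to the secondary-endpoint ADE analyses.
- A reader might infer a clash with Protocol 10.12.3: "All data available through the time of the subject's exit will be used for analysis". That conflict is only indirect, because pregnancy is not among the exit reasons listed there.
- Current or planned pregnancy is an exclusion criterion (Protocol 9.4), so few cases are likely. The usual case, a recurrence-free woman, moves the rate slightly upwards. Even the loss of one recurrence lies well inside the planned half-width of 3.6 to 4.4 points, and the analysis is descriptive with no success threshold to cross.
- The instructions for use state that safety and effectiveness in pregnant women have not been established. That gives some reason to look at these subjects separately, but not to remove what was observed before the pregnancy.

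None of this removes the conflict. Following the SAP avoids the deletion only by departing from a protocol sentence that SAP 7.12 does not record as changed, although Protocol 14.1 asks for such changes to be documented.

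**Conclusion.** The point holds as a conflict to be resolved before the data are analysed. Protocol 14.4, applied as written, makes the 12-month result depend on a later event and can drop an observed recurrence, contrary to Protocol 14.3.1 and to the SAP's FAS and formula. The likely effect is small: about 0.8 to 1.0 point lower for each recurrence lost, and about 0.03 to 0.05 point higher for each recurrence-free subject lost. A shift of any note from a single subject would therefore run in the device's favour. These sizes rest on an assumed 4 or 5 recurrences among 100 or 125 subjects and on one pregnancy at a time, since the documents give no count. If no subject becomes pregnant, the results do not differ at all. The change is worth making because it is cheap and the present texts cannot both be followed.

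**What to change.** Delete the exclusion sentence from Protocol 14.4 and state one rule there and in the SAP (7.4 or 7.9):

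- Subjects who become pregnant after surgery stay in the full and safety analysis sets.
- Every recurrence within 12 months, and every ADE in the relevant window, counts under the same formula as for other subjects, whether it came before or after the pregnancy.
- A recurrence-free subject stays in the 12-month denominator if she has at least 12 months of follow-up, as SAP 7.9 already requires of everyone. This settles the case of a pregnancy before month 12.
- If any such subject exists, show a sensitivity analysis that censors at documented pregnancy or excludes these subjects. Neither should be the main analysis: using only data up to the pregnancy would drop a recurrence diagnosed after it but still within 12 months, which Protocol 14.3.1 counts.

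The cost is a short edit to each document and at most one extra table, with no new data. The protocol edit may need sponsor and IRB review under Protocol 16.6. If it has to wait, Protocol 14.1 allows the change to be recorded in the SAP and the clinical study report, and SAP 7.12 is the natural place.
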